After obtaining consent and ensuring all inclusion and exclusion criteria are met, randomization will be done in the emergency room prior to treatment using a web-based dynamic randomization system. Our randomization algorithm will be accessible to the study investigators and staff through a separate web page accessible only through the REDCAP database module. Covariate adaptive randomization will be used to balance the distribution of age (<60, 60-69, 70-79, 80-85 years old), presentation NIHSS (6-9, 10-15, 16-20, >20), center, clot location (M1, ICA), treatment time window (0-8, 9-16, 17-24 hours from onset to randomization time), CTP/MRP core volume (<50cc, 50-100cc, >100cc), presence or absence of target mismatch profile (mismatch ratio ≥ 1.8 & mismatch volume ≥ 15 cc) and hemisphere (right, left) between the two treatment groups.

The randomization algorithm we are going to implement is the algorithm developed by Pocock and Simon (1975)²⁷, i.e., minimization method. Through this algorithm, the assignment of a new patient to a treatment group is determined so as to minimize the differences between the groups in terms of these important key baseline variables. Unlike traditional stratified randomization, the minimization method works toward minimizing the total imbalance for all factors together instead of considering mutually exclusive subgroups, that is, we will not be creating these mutually exclusive subgroups during the randomization. Therefore, this approach is not restricted by the number of variables and the possible combinations of levels of balancing factors. Further details about Randomization can be found in Appendix A.

Eligible patients will be randomized into thrombectomy plus medical management vs medical management alone at a 1:1 ratio. The minimization algorithm is intended to balance the baseline characteristics between the two study arms, thrombectomy vs. medical management. The algorithm is not intended at the level of imaging profile subgroup. When a new patient is enrolled, the site will enter the stratification factor values into the dynamic randomization webpage and the treatment assignment will be determined immediately. An emergency 1-800 number will be provided if web-based randomization is not available due to exigent circumstances.

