investigators may also use devices for angioplasty or for stenting of the carotid artery as deemed appropriate. The use of adjuvant intra-arterial (IA) thrombolytic medication is not currently approved by the FDA for stroke treatment and cannot be used in SELECT 2.

Sites will use local protocols for femoral access, sedation, heparin infusion, monitoring, etc. Sites will perform a cervical injection of the involved carotid circulation as a baseline angiogram. At the conclusion of the procedure, a post-treatment angiogram as a cervical injection of the involved carotid circulation will also be obtained. Imaging will cover the full region of the normal circulation in AP and lateral projections at 2-3 films per second through the entire venous phase. All brain imaging from stroke onset through hospital discharge, including the MRI, CTP/MRP, and CT, as well as angiographic images obtained for the diagnostic and therapeutic portions of the procedure, will be transmitted to the core lab. The use of general anesthesia is left to the local investigators but discouraged by the study given the concerns of worse outcomes associated with that.

In cases of extracranial ICA occlusions, immediate stenting will be discouraged and delayed stenting (beyond 72 hours) will be preferred to reduce the risk of hemorrhagic transformation because of requirements of antiplatelet therapy/heparin to prevent re-occlusion.

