3.7.1.3. Imaging Outcomes

Imaging endpoints are: 1) infarct volume on MRI DWI sequence (or CT if MRI not feasible) 24 hours to 7 days after randomization; 2) lesion growth between the RAPID identified ischemic core on baseline imaging and the infarct volume; 3) successful reperfusion defined as DWI lesion volume minus $T_{max} > 6$ seconds greater than 50%; and 4) the proportion of subjects with recanalization of the primary arterial occlusive lesion. The technical efficacy of the endovascular procedure will be assessed by a modified Thrombolysis in Cerebral Infarction scores of 2b (50% to 75% reperfusion), 2c (>75% to 99% reperfusion) or 3 (complete reperfusion).²²

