Secondary analyses: Our secondary endpoint is the proportion of patients with mRS 0-2 at day 90 (indicating functional independence). The difference in the proportions of patients with mRS 0-2 between treatment arms will be assessed using logistic regression. We will adjust for the variables we used in adaptive randomization program in the logistic regression model. Other secondary endpoints include (1) the safety outcomes measured by the incidence of sICH, neurological worsening, mortality, groin hematomas, infections or vascular injury, (2) infarct volume, lesion growth, successful reperfusion, and recanalization rate, (3) length of hospital stay, and (4) discharge disposition. The exploratory analyses on secondary outcomes will include descriptive statistics (mean [\pm standard deviation, SD] or median and interquartile range for continuous variables and frequency [percentage] for discrete variables) and appropriate test for secondary outcome variables between two groups. For binary outcomes (e.g., sICH, neurological worsening, mortality, groin hematomas, infections or vascular injury, successful reperfusion, recanalization), Chi-square or Fisher's exact test where appropriate will be used to compare the incidence between two treatment groups for large core patients. We will also apply the logistic regression model on these outcomes after adjusting for the variables we used in adaptive randomization program. The adjusted odds ratio (OR), as well as 95% confidence interval will be reported. For the length of stay, mean \pm SD and median (Interquartile range) will be calculated for each group. For continuous variables (e.g., the length of stay and infarct volume), two sample t-test or Wilcoxon rank sum test as appropriate will be applied to compare them between two groups. For discharge disposition, frequency and percentage of each disposition will be reported and Chi-square test or Fisher's exact test where appropriate will be applied to compare its distribution between two groups.

Subgroup analyses: Subgroup analyses of the effect of thrombectomy on the primary and secondary endpoints will be performed. Subgroups will be defined based on the stratification variables, key demographic factors (such as race and ethnicity), thrombolysis vs. no thrombolysis, CTP vs. MRI selection, and witnessed vs. unwitnessed symptom onset, wake-up vs non-wake-up stroke, and TIC1 0-2a vs. TIC1 2b/3 results in the cath lab. An additional

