All baseline and follow-up CTs, CT-Angiograms (CTAs) and CTP/MRP images will be reviewed by a central lab core at UTH. [name], Associate Professor, Diagnostic and Interventional Imaging and [name], Professor, Diagnostic and Interventional Imaging at UT McGovern Medical School will serve on the imaging core lab. All images will be sent to the central lab core in a de-identified manner. All radiology interpretations will occur independently of any knowledge of clinical factors. Blinding of imaging core lab at UT Houston will be ensured. We have several neuroradiologists at the institute and the neuroradiologist for the core lab will not participate in the care of a patient enrolled in the trial. Also, the neuroradiologists, while evaluating images will assess the CT images at a different time than the MRIs. They will also not be aware of the treatment and other clinical variables.

A) Parenchymal (e.g., non-contrast head CT) Imaging - the ASPECT score will be determined (baseline study only). Follow up studies will be determined for stroke location as well as for the presence of any hemorrhage and hemorrhage grading.

B) CT-Angiograms of the head – identify the vessel occlusion location and collateral scoring system.

C) CTP-Advanced analysis through the RAPID software (RAPID, non-commercial research version iSchemaView, Inc.) will be utilized to identify potentially salvageable brain tissue. Brain tissue at risk for infarction will be distinguished from minimally hypo-perfused tissue if the time to maximum (Tmax) delay is more than 6 seconds. Irreversibly injured brain (hypo-perfused tissue will be diagnosed if the relative cerebral blood flow is less than 30% of that in normal tissue.

D) Conventional Angiograms – identify and grade reperfusion using the modified TIC1 scoring system.

12. National Data Management Center

Data management and site monitoring will be performed by the University of Texas at Houston (UTH). The UTH will create the database and set up the interface on the REDCAP where clinical site personnel will enter the data into the electronic CRF. Data quality assurance processes include: (1) logic and rule checks built into the database; (2) monitoring by the Data Manager at the UTH; (3) central monitoring by the statistical programmer at the UTH; and (4) risk-based source verification monitoring by the Study Coordinators.

13. Data Management Plan

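### TICI grade arises after randomisation and only from the catheter angiogram, so it cannot define a subgroup for the effect of thrombectomy

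*Combined protocol and SAP*

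**What the plan says.** The subgroup paragraph of Section 6.1 opens with "Subgroup analyses of the effect of thrombectomy on the primary and secondary endpoints will be performed". Its list mixes baseline factors with one procedural result: "wake-up vs non-wake-up stroke, and TIC1 0-2a vs. TIC1 2b/3 results in the cath lab". It names no comparator for the TICI split and does not describe that split as descriptive or confined to the EVT arm.

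Other sections fix when and where TICI arises:

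- Section 3.3/3.4 (Enrollment and Randomization): "randomization will be done in the emergency room prior to treatment using a web-based dynamic randomization system".
- Section 3.5 (Endovascular Thrombectomy): "At the conclusion of the procedure, a post-treatment angiogram as a cervical injection of the involved carotid circulation will also be obtained".
- Section 11 (Imaging Core Lab), under conventional angiograms: "identify and grade reperfusion using the modified TIC1 scoring system".
- Section 3.7.1.3 (Imaging Outcomes): "The technical efficacy of the endovascular procedure will be assessed by a modified Thrombolysis in Cerebral Infarction scores".

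The secondary analyses in Section 6.1 include groin hematoma, infections or vascular injury, successful reperfusion and recanalization among the binary outcomes. For these, Chi-square or Fisher tests "will be used to compare the incidence between two treatment groups for large core patients". Logistic regression adjusted for the randomisation variables follows, with odds ratios and 95% CIs. Section 3.7.1.2 defines recanalization on the modified TICI scale.

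**The concern.** A subgroup analysis of a treatment effect compares the randomised arms within a level of a variable that both arms have and that treatment cannot change. TICI fails on both counts. Within TICI 2b/3 there is no MM group to compare with, apart from any crossovers, who are themselves selected.

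If the analysis is forced by setting TICI-selected EVT patients against MM patients, only one side has been filtered on procedural success. If patients who reperfuse would have done better anyway, the 2b/3 contrast drifts towards benefit and the 0-2a contrast towards harm, even with an ineffective treatment. Listed beside age and NIHSS as a prespecified subgroup, the result could be read as randomised evidence that reperfusion causes the benefit.

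A smaller matter is that some secondary outcomes are tied to the procedure. Between-arm p-values and odds ratios for events that are near zero in MM by design say little.

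**Working it through.** **Where TICI exists.** Randomisation precedes treatment (Section 3.3/3.4). The post-treatment angiogram is taken when the procedure ends (Section 3.5), and TICI is graded on conventional angiograms (Section 11). TICI is therefore post-randomisation and absent in MM except in crossovers. With no MM variation in TICI, a treatment-by-TICI term has no estimate.

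**Check of the inputs against the plan's own figure.** Section 6.1 projects mRS 0 to 6 as 4/8/12/16/19/13/28% for EVT and 1/4/9/14/19/10/43% for MM.

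- P = P(EVT better) + ½P(tie) = 0.59375.
- With p̄ the average of the two arms' proportions, Σp̄³ = 0.0579.
- N = (1.960 + 1.282)² × (1 − Σp̄³) / [3(P − 0.5)²] = 10.507 × 0.9421 / (3 × 0.008789) = 375.4, so 376.

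This reproduces the stated 376 (188 per arm), so the distributions and the Wilcoxon test are read as the plan intends.

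**Size of the bias if TICI-selected EVT patients are compared with all MM patients.** The documents give neither a 2b/3 rate nor a TICI-prognosis correlation, so both are assumptions. Setup: 280 per arm (the maximum EVT arm in Section 10 and 1:1 allocation), and the MM mRS distribution in both arms, so no EVT effect. TICI success is a threshold on a normal variable that has correlation r with a latent prognosis. The test is the tie-corrected Wilcoxon, with 4,000 simulated trials per setting. Nominal one-sided error is 2.5%.

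| Assumed 2b/3 rate | r | False benefit, 2b/3 vs MM | False harm, 0-2a vs MM |
|---|---|---|---|
| 70-90% | 0 | 2.3-2.6% | 2.2-2.5% |
| 70% | 0.2 | 15.2% | 40.2% |
| 80% | 0.2 | 10.4% | 39.6% |
| 90% | 0.2 | 6.3% | 32.4% |
| 70% | 0.4 | 47.0% | 94.2% |
| 80% | 0.4 | 27.9% | 95.1% |
| 90% | 0.4 | 12.0% | 89.7% |

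**Hand check of the 80%, r = 0.2 row.** The simulated mean P is 0.517 for 2b/3 and 0.431 for 0-2a, which is 0.017 and 0.069 from 0.5. The tie factor for the MM distribution is 1 − Σp³ = 0.909. The expected |Z| is |P − 0.5| × √[12·n₁·n₀ / ((n₁ + n₀ + 1) × 0.909)].

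- 2b/3 (n₁ = 224, n₀ = 280): 0.017 × 40.5 = 0.69, and Φ(0.69 − 1.96) = 10%.
- 0-2a (n₁ = 56, n₀ = 280): 0.069 × 24.8 = 1.71, and Φ(1.71 − 1.96) = 40%.

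In this setting true mRS 0-2 is 14% in both arms, but the split shows 15.5% for 2b/3 and 8.4% for 0-2a.

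**Smaller trial.** Table 3 gives an average of 426 randomised under the null, or 213 per arm. The same formula with n₁ = 170.4 and 42.6 gives 0.017 × 35.3 = 0.60, so about 9%, and 0.069 × 21.6 = 1.49, so about 32%.

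**Procedural events.** With 0/280 in MM, Fisher's exact test gives p = 0.061 for 5 EVT events and p = 0.030 for 6 (6/280 = 2.1%). A logistic fit with 14/280 versus 0/280 fails because of separation, so no finite maximum-likelihood odds ratio exists.

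**Recanalization.** An mTICI grade of 2b or better in 70-90% of EVT patients against 0 in MM gives p < 10⁻⁸⁰, where the zero reflects the absence of an angiogram. Table 2 schedules MRI, or CT if MRI is not feasible, at 24 hours to 7 days, and names no follow-up CTA, MRA or perfusion study.

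**The case against.** The plan never says that TICI-selected EVT patients will be compared with all MM patients. A within-EVT comparison of 0-2a with 2b/3 is equally computable, and the reference to the cath lab fits it. This stands: a reader might infer that the plan prescribes the biased contrast, but the text only leaves the comparator undefined under a heading that promises treatment effects. The simulation shows what one natural reading would produce.

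The size of the bias rests wholly on assumption. This also stands. At zero correlation there is none, and the large figures come from the upper end of an arbitrary range.

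A reader might also infer that the between-arm comparison of procedural events is biased, or that such events cannot occur or go unmeasured in MM. The documents do not support that. Section 15 has intra-procedural complications assessed in both arms, and Section 5 and Table 2 track crossovers. An intention-to-treat count of access-site events validly describes added procedural risk. Nor is significance automatic, since 5 events against 0 gives p = 0.061. What remains is that the test says little and the odds ratio may be inestimable.

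Non-catheter assessment of recanalization in MM is not ruled out. Section 3.7.1.3 lists recanalization of the occlusive lesion apart from mTICI technical efficacy, and Section 11 has the core lab read follow-up CTAs. Successful reperfusion has a DWI/Tmax definition that is not EVT-only. A between-arm comparison should stay open where both arms have the same imaging.

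Finally, Section 6.1 calls the secondary-outcome analyses exploratory. That limits the consequences, but it does not give MM patients a TICI grade.

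**Conclusion.** The point holds for the TICI subgroup, and nothing elsewhere in the documents repairs it. A grade that arises after randomisation, from a procedure that only one arm is assigned, cannot define a subgroup for the effect of thrombectomy. Any contrast of TICI-selected EVT patients with MM breaks the randomisation. The direction of bias follows from reperfusion success being related to prognosis. Its size, about 10% false benefit and 40% false harm at the illustrative setting, depends on an assumed 2b/3 rate and correlation that the documents do not supply.

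The point on secondary outcomes is narrower. An mTICI-based between-arm test of recanalization is not interpretable with no angiogram in MM. Tests and adjusted odds ratios for access-site and procedural vascular events are uninformative or inestimable when MM events are near zero by design.

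It would be wrong to infer that the trial's main conclusions are at risk. The primary mRS test, the sample size, the boundaries in Appendix B and the safety rules in Section 10 use neither TICI nor these tests.

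**What to change.** 1. Delete TICI from the treatment-effect subgroups in Section 6.1. Report outcomes by TICI grade descriptively within the EVT arm, labelled as a non-randomised comparison.
2. Report mTICI recanalization as an EVT-arm proportion with a 95% CI. Compare recanalization or reperfusion between arms only where the same follow-up imaging is available in both, and name that imaging.
3. Report access-site hematoma and procedural vascular injury as counts and rates with 95% CIs by randomised arm, so that events in crossovers are kept, without significance tests or adjusted odds ratios.

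The cost is SAP wording only. No patients or data are added, fewer analyses are run, and the 376, the 560 and the boundaries do not change.

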6.2. Statistical plan for the second aim

The second aim is to compare outcomes in patients with discordant imaging profiles. Good outcome rates (90-day mRS 0-2) will be compared between EVT patients with favorable CTP/unfavorable CT and EVT patients with unfavorable CT/favorable CTP. Logistic regression model will be applied and odds ratio as well as 95% CI will be calculated. If there is a significant difference in the outcome, we will evaluate whether any patient characteristics could be potential confounders and can explain these differences.

We will also assess the heterogeneity of the treatment effect of thrombectomy comparing to medical management between patients with favorable CT/unfavorable CTP and patients with unfavorable CT/favorable CTP. We will assess the heterogeneity by evaluating the interaction effect in the logistic regression model between treatment groups (EVT vs MM) and imaging profile (favorable CT/unfavorable CTP vs unfavorable CT/favorable CTP). If the interaction term is statistically significant, we will examine patient characteristics and other baseline clinical characteristics for possible correlations or confounding factors.

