3.7. Outcome Measures

3.7.1.1. Primary Outcome

The primary outcome #1 will be the distribution of mRS scores at 90 days. The primary outcome #2 will be the percentage of good outcome (mRS 0-2) at 90 days. The definition of favorable primary clinical outcomes is the patients' functional outcomes at 90 (+/- 15) days, measured by a modified Rankin scale (mRS) score of 0-2. The determination of mRS scores will be performed by certified raters unaware of the treatment arm or the baseline clinical and radiographic characteristics of the individual patient by in person interview or by telephone if in-person visit is not possible.

The shift in the modified Rankin Scale score is better equipped to capture potential improvement in the functional outcomes as compared to a binary (dichotomized) outcome with intervention. Since the study population is composed of acute stroke patients with significant ischemic changes (unfavorable imaging profiles), the potential shift across modified Rankin Scale Score categories, not only the functional independence, is of clinical significance. For details, a change of mRS score of 5 – completely bedridden to mRS score of 4 – ambulating with a wheelchair and to mRS score of 3 – ambulating with a cane is a successful outcome for thrombectomy. We will still have the dichotomized outcome as our second primary outcome.

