Considering a prior assumption that the EVT effect is largest in the patients with good imaging profile and treated within the shortest time window, we assume that the highest effect of EVT will be observed in G1A. Then the effects get decreased gradually in G1B, G2A, G2B, G3A, and the lowest effect will be observed in G3B. According to this adaptive design, when a most promising subgroup needs to be selected at the time of interim (or final) analysis, we will compare the GLR statistic among five cumulative groups, that is, G1A, G1A+G1B (i.e., Group 1), G1A+G1B+G2A, G1A+G1B+G2A+G2B (i.e., Group 1+Group 2), and G1A+G1B+G2A+G2B+G3A.

Primary analysis: The primary endpoint is the distribution of scores on the modified Rankin Scale (mRS) at day 90. The null hypothesis will be tested at the interim and final analysis using a normal approximation of the Wilcoxon-Mann-Whitney test (the GLR test). The principle of the intention to treat will be applied for the primary analysis. An additional analysis of the primary endpoint will be the same rank-based analysis comparing the 90-day mRs distribution between treatment groups while stratifying for prognostically important covariates. We will use the Generalized Cochran-Mantel-Haenszel test (CMH) to evaluate whether there is a uniform shift on the mRS distribution from one group to the other after stratification. The CMH test will be stratified by these variables used in the covariate adaptive randomization. For age, NIHSS, treatment time window, and CTP core volume, we will consider them as continuous variables in this adjusted analysis.

Power and sample size considerations Based on prior reported data, the following distributions were projected on the mRS at 90 days in EVT and MM groups for SELECT 2 in the overall population.

	mRS at day 90							Total
	0	1	2	3	4	5	6	
Endovascular group	4%	8%	12%	16%	19%	13%	28%	100%
Medical group	1%	4%	9%	14%	19%	10%	43%	100%

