This distribution corresponds to a standardized effect of 0.34 for the primary analysis. Based on these data, the fixed sample size for a non-adaptive design requires a total of 376 patients (188/arm) to have 90% power at an alpha of 5% (Wilcoxon-Mann-Whitney test); We add additional 184 patients for the adaptive design to reach a maximum sample size of 560. We will conduct two interim analyses when we reach the number of patients at 200 and 380. Through extensive simulation studies, we have shown that with 560 patients in total for the adaptive design, we will have around 91% power to test for a standardized effect size of 0.34 in the overall population (assuming homogeneous EVT effect across six disjoint groups) by controlling an overall (one-sided) Type I error rate at 2.5%.

Efficacy and futility bound At each analysis (two interim analyses and the final analysis), an efficacy bound will be set to decide if the study should be stopped for efficacy while controlling the overall (one-sided) Type I error rate at 2.5%. At each interim analysis, a futility bound will be set to decide if the study should continue recruitment in the overall group, shift accrual and testing to a subgroup, or stop the trial entirely. When the futility bound is crossed and the optimal subgroup is selected, the maximum analyzed sample size will not be fixed but a random variable (smaller than the fixed maximum sample size 560). Due to the reduction in the maximum number of patients available for analysis at the end of the study, our design allows

an easier futility stop after subgroup selection. Further details regarding efficacy and futility bounds at interim and final analyses is provided in Appendix B.

First interim analysis (n=200 randomized and completed 90-day follow-up): The null hypothesis is tested in the entire patient cohort:

1. If neither efficacy nor futility bound is crossed, the trial continues enrollment to the 2nd interim analysis.
2. If the efficacy bound is crossed, the trial stops and efficacy is declared in the overall cohort.
3. If the futility bound is crossed, the optimal subgroup is selected based on the GLR statistic and the null hypothesis is tested in this selected subgroup:
 - 3.1. If neither bound is crossed, the trial will continue with enrollment limited to the selected subgroup
 - 3.2. If the efficacy bound is crossed, the trial stops and efficacy is declared in the selected subgroup

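### The second-aim comparison of imaging profiles names no covariates and examines confounding only after a significant result, so a difference hidden by imbalance would usually go unexamined

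*Combined protocol and SAP*

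**What the plan says.** Section 6.2 has two analyses for the second aim.

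- **Comparison across profiles.** mRS 0-2 at 90 days is compared between thrombectomy patients of the two discordant profiles by logistic regression, reporting an odds ratio and 95% CI. No covariates are listed. The next step is conditional: "If there is a significant difference in the outcome, we will evaluate whether any patient characteristics could be potential confounders". (The sentence that defines the groups names the same profile twice. I read it, with Section 2, as favorable CT/unfavorable perfusion against unfavorable CT/favorable perfusion.)
- **Heterogeneity of treatment effect.** This is assessed "by evaluating the interaction effect in the logistic regression model between treatment groups (EVT vs MM) and imaging profile". The outcome is not named. Baseline characteristics are again examined only if the interaction is significant.

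Three other places bear on this. Section 1.5 says how a null result will be read: if the difference does not reach the 15% margin, outcome rates are taken not to differ, and if there is no heterogeneity, benefit is taken not to be modified. Section 6.1 (Secondary analyses) adjusts the logistic model of mRS 0-2 between randomised arms for the minimisation variables. Section 3.7.1.1 says of the overall trial: "The shift in the modified Rankin Scale score is better equipped to capture potential improvement in the functional outcomes".

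**The concern.** Imaging profile is a baseline trait. Age, time from last known well, clot location and severity may differ between the two profiles, and such differences can mask a contrast as easily as produce one. A rule that opens the question of confounding only after significance deals with the second case and never with the first. That would matter less if a null result were left uninterpreted, but Section 1.5 draws a conclusion from it. The plan also prespecifies adjustment where arms are randomised and confounding is least likely, and names none where groups are not randomised.

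A smaller point concerns the interaction. Its outcome has to be inferred. If it is mRS 0-2, the test uses the less informative form of the scale in groups of about 112 patients.

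**Working it through.** **1. The plan's own figure.** Section 6.1 projects "Endovascular group 4% 8% 12% 16% 19% 13% 28% 100" and "Medical group 1% 4% 9% 14% 19% 10% 43% 100" (mRS 0 to 6, per cent) and states that a fixed design "requires a total of 376 patients (188/arm) to have 90% power at an alpha of 5% (Wilcoxon-Mann-Whitney test". From these columns, θ = P(thrombectomy better) + ½P(tie) = 0.59375. The pooled distribution p̄ is 2.5, 6, 10.5, 15, 19, 11.5, 35.5%, so Σp̄³ = 0.0579. The tie-corrected Noether formula gives

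N = (1.960 + 1.282)² × (1 − 0.0579) / (3 × 0.09375²) = 375.4,

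which reproduces 376. The projected columns can therefore be used below. Section 6.2 gives no sample size or power of its own.

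**2. Group sizes.** Table 3 assumes 14% + 6% of patients in each discordant group. 20% of 560 is 112 per profile, and 1:1 allocation gives 56 thrombectomy patients per profile. This assumes full enrolment at those proportions.

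**3. Power of the comparison.** Section 1.5 gives 48% and 32% from the earlier cohort.

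- SE = √(0.48×0.52/56 + 0.32×0.68/56) = 0.0913
- Power = Φ(0.16/0.0913 − 1.96) = Φ(−0.21) = 0.42 (0.41 with the pooled null variance)
- At 40 per group power is 31%, and at 84 per group 56%. 80% power needs 146 per group.

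So the chance of the branch in which confounders are not examined is about 58% when the assumed difference is real and nothing masks it.

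**4. Effect of masking (assumption).** The documents report no imbalance between profiles. For illustration, suppose imbalance hides 4 or 8 of the 16 points:

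- 4 points: Φ(0.12/0.0913 − 1.96) = 0.26
- 8 points: Φ(0.08/0.0913 − 1.96) = 0.14

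The more a difference is masked, the less likely the plan is to look for the cause.

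**5. The interaction: mRS 0-2 against the full scale.** Information on the log odds ratio per profile (N = 112) is N/12 × (1 − Σp̄³) for the ordinal scale and N/4 × p(1 − p) for mRS 0-2. With equal information I in both profiles, the interaction SE is √(2/I).

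*Overall projection (p = 0.19 in both profiles).* Ordinal: 112/12 × 0.9421 = 8.79. Binary: 112/4 × 0.19 × 0.81 = 4.31. The ratio is 0.49 and the interaction SEs are 0.477 and 0.681.

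*Cohort rates.* Here I rescale the projected columns so that mRS 0-2 is 48% or 32% under thrombectomy and 13% under medical management. The 13% is the Section 1.1 figure for patients unfavorable on one or both modalities, so using it for each discordant group is an assumption. Pooled p is 0.305 and 0.225. Ordinal information is 8.93 and 8.84; binary is 5.94 and 4.88. The ratios are 0.66 and 0.55 (0.67 and 0.56 if medical management is 14%). The interaction SEs are √(1/8.93 + 1/8.84) = 0.474 and √(1/5.94 + 1/4.88) = 0.611.

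| Assumed rates | Ratio of ORs | Ordinal power | mRS 0-2 power |
|---|---|---|---|
| Overall projection | 2 | 31% | 17% |
| Overall projection | 3 | 63% | 36% |
| Cohort rates | 2 | 31% | 20% |
| Cohort rates | 3 | 64% | 44% |

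Each entry is Φ(ln(ratio)/SE − 1.96). It assumes proportional odds, so that the same ratio applies on both scales. The projected columns are not proportional: their cumulative odds ratios run from 1.62 to 4.13.

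**The case against.** The second aim is framed as a correlation of imaging profile with outcome. For a purely prognostic question, the crude difference among eligible treated patients is a legitimate quantity. NIHSS may partly reflect infarct extent, so adjusting for it could remove some of the contrast under study. Both points stand. They argue for reporting the crude estimate beside the adjusted one and for showing NIHSS in and out. They do not support making the choice depend on a p-value.

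Four stronger readings are tempting, and the documents do not support them.

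- *That Section 6.2 rules out adjustment.* It does not. It specifies a logistic model and is silent on covariates.
- *That confounding will produce false findings.* The plan already follows up a significant result by looking for confounders. Only the masking side is left open.
- *That the randomisation section shows the profiles will be unbalanced.* Its statement "The algorithm is not intended at the level of imaging profile subgroup" concerns balance between arms. Even perfect arm balance within each profile would not make thrombectomy patients in one profile comparable with those in the other.
- *That the interaction test discards half the information.* The outcome is inferred to be mRS 0-2. A ratio near one half holds at the overall projection but rises to about 0.67 at the cohort rates. mRS 0-2 is also a declared endpoint: the second primary outcome and the endpoint of part A of the second aim. The stated preference for the shift concerns the primary outcome.

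Treatment is randomised within each profile, so for the interaction confounding bears only on whether a difference in effect can be attributed to imaging.

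**Conclusion.** The point holds for the conditional rule. Section 6.2 makes a non-randomised comparison with no named covariates, examines confounding only after significance, and feeds a conclusion that Section 1.5 draws from a null result. At about 42% power, the unexamined branch is the likelier one even if the assumed 16-point difference is real. This rests on 56 thrombectomy patients per profile and the cohort rates. Early stopping or enrichment would change the group sizes. The direction does not depend on the 4-8 point illustration. The low power comes from group size, and adjustment will not cure it.

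For the interaction, the defect is an unnamed outcome. An ordinal version is a useful addition rather than a correction. Its gain depends on proportional odds, and at 31% power for a ratio of 2 it remains exploratory.

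**What to change.** In Section 6.2:

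1. Report crude and adjusted estimates whatever the crude p-value. Adjust for age, time from last known well and clot location, and show the result with and without NIHSS. Do not adjust for ASPECTS or core volume, which define the groups.
2. Because an odds ratio can shift on adjustment without any confounding, also give both contrasts as risk differences with 95% CIs, the scale of the Section 1.5 margin. Tie the Section 1.5 conclusion to those intervals.
3. Name the outcome of the arm-by-profile interaction. Fit it both for mRS 0-2 and as a proportional-odds model of the full 90-day mRS, and label both exploratory.
4. Correct the sentence that names one profile twice.

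The cost is SAP wording. The covariates are already collected, and no patients or visits are added. About 45 good outcomes are expected (56×0.48 + 56×0.32 = 44.8), so the covariate list should stay this short. The ordinal interaction relies on proportional odds, and the mRS 0-2 version serves as its check.
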